### **6.3 General Concomitant Medication and Supportive Care Guidelines**

Because there is a potential for interaction of entinostat with other concomitantly administered drugs, the case report form must capture the concurrent use of all other drugs, over-the-counter medications, or alternative therapies. The Principal Investigator should be alerted if the patient is taking any agent known to affect or with the potential for drug interactions. The study team should check a frequently-updated medical reference for a list of drugs to avoid or minimize use of. Appendix C (Patient Drug Interactions Handout and Wallet Card) should be provided to patients if available.

After Cycle 1, certain forms of radiotherapy may be considered for pain palliation if patients are deriving benefit (e.g., treatment of known bony metastases); administration of study drugs may be suspended during radiotherapy.

#### **6.3.1 Entinostat**

##### **6.3.1.1 Concurrent Medications**

Caution is warranted when administering entinostat to patients taking drugs that are highly dependent on CYP2B6 and CYP3A4 for metabolism and have a narrow therapeutic index.

*In vitro* studies show that entinostat is not metabolized by CYP enzymes, but rather by UGT 1A4 to form a glucuronide metabolite. Data from *in vitro* experiments showed that, while entinostat inhibited cytochrome P-450 (CYP) enzymes 2C8 and 3A4, the degree of the inhibition makes it unlikely that any *in vivo* systemic interactions would occur. Entinostat did not inhibit any tested UDP glucuronosyltransferase (UGT) enzymes. However, entinostat has the potential to induce CYP 1A2 and CYP 2C8. Finally, entinostat is a substrate for P-glycoprotein (P-gp) and breast cancer resistance protein (BCRP) transporters and does not inhibit either of these transport proteins

Caution is warranted when administering entinostat to patients taking CYP2C8 substrates. *In vitro* study results indicate that entinostat has the potential to inhibit CYP2C8.

##### **6.3.1.2 Contraindications, Warnings, and Precautions**

The following should be observed in all clinical settings with entinostat administration:

1. Administration of entinostat is contraindicated in patients with a history of allergy to entinostat or other medications that have a benzamide structure (e.g., tiapride, remoxipride, clebropipride).

2. Careful monitoring of patients for signs of infection or reactivation of past infections is recommended, as reactivation of infection has been reported in patients treated with entinostat, in some cases without evidence of neutropenia (Gojo *et al.*, 2007). The clinical significance of this finding and the potential association with entinostat is unknown.

#### 6.3.1.3 Overdose

Doses in excess of 12 mg/m^2 have not been evaluated clinically. Risk of overdose may be minimized by providing careful instructions to patients on dosing as well as compliance assessments that include diaries and pill counts.

No antidote for entinostat is available. It is not known if entinostat is removed from the blood by hemodialysis, charcoal hemoperfusion, or peritoneal dialysis.

Overdoses should be managed with supportive care as appropriate.

#### 6.3.2 Atezolizumab

##### 6.3.2.1 Atezolizumab General Concomitant Medication Guidelines

Patients who experience infusion-associated symptoms may be treated symptomatically with acetaminophen, ibuprofen, diphenhydramine, and/or cimetidine or another H2 receptor antagonist, as per standard practice (for sites outside the United States, equivalent medications may be substituted per local practice). Serious infusion associated events manifested by dyspnea, hypotension, wheezing, bronchospasm, tachycardia, reduced oxygen saturation, or respiratory distress should be managed with supportive therapies as clinically indicated (*e.g.*, supplemental oxygen and  $\beta_2$ -adrenergic agonists; see **Section 6.1.2**).

Systemic corticosteroids and tumor necrosis factor alpha (TNF) $\alpha$  inhibitors may attenuate potential beneficial immunologic effects of treatment with atezolizumab but may be administered at the discretion of the treating physician. If feasible, alternatives to corticosteroids should be considered. Premedication may be administered for Cycles  $\geq 2$  at the discretion of the treating physician. The use of inhaled corticosteroids and mineralocorticoids (*e.g.*, fludrocortisone) for patients with orthostatic hypotension or adrenocortical insufficiency is allowed. Megestrol administered as appetite stimulant is acceptable while the patient is enrolled in the study.

Patients who use oral contraceptives, hormone-replacement therapy, prophylactic or therapeutic anticoagulation therapy (such as low-molecular-weight heparin or warfarin at a stable dose level), or other allowed maintenance therapy [*describe here*, if applicable] should continue their use. Males and females of reproductive potential should use highly effective means of contraception.

### 6.3.2.2 Atezolizumab Excluded Therapies

Any concomitant therapy intended for the treatment of cancer, whether health authority approved or experimental, is prohibited unless it is specifically included in the treatment regimen described in this protocol. This includes but is not limited to the following: Chemotherapy, hormonal therapy, immunotherapy, radiotherapy, investigational agents, or herbal therapy (except for maintenance therapies outlined in **Section 6.3.2.1**).

It is strongly recommended that:

- Traditional herbal medicines not be administered because the ingredients of many herbal medicines are not fully studied and their use may result in unanticipated drug drug interactions that may cause, or confound assessment of, toxicity.
- The use of a RANKL inhibitor (denosumab) be discontinued during the study; this agent could potentially alter the activity and the safety of atezolizumab.
- Initiation or increased dose of granulocyte colony stimulating factors (*e.g.*, granulocyte colony stimulating factor, granulocyte/macrophage colony stimulating factor, and/or pegfilgrastim) is prohibited for patients with solid malignancies.
- Patients are not allowed to receive immunostimulatory agents, including, but not limited to, interferon-alpha (IFN- $\alpha$ ), IFN-gamma( $\gamma$ ), or interleukin (IL)-2, during the entire study. These agents, in combination with atezolizumab, could potentially increase the risk for autoimmune conditions.
- Patients should also not be receiving immunosuppressive medications, including, but not limited to, cyclophosphamide, azathioprine, methotrexate, and thalidomide. These agents could potentially alter the activity and the safety of atezolizumab. Systemic corticosteroids and anti-TNF $\alpha$  agents may attenuate potential beneficial immunologic effects of treatment with atezolizumab but may be administered at the discretion of the treating physician. If feasible, alternatives to these agents should be considered.

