### 3. PATIENT SELECTION

#### 3.1 Eligibility Criteria

3.1.1 Patients must have histologically or cytologically confirmed extensive stage SCLC (ES-SCLC) or other solid tumors for which carboplatin and etoposide are considered appropriate therapy.

3.1.2 No prior systemic therapy for extensive-stage, metastatic disease. Patients with prior limited stage disease who were treated with chemotherapy and concurrent radiation will be permitted to enroll as long as their previous treatment was 12 months or more prior to study enrollment.

3.1.3 Patients with **treated brain metastases** are eligible if they have stable symptoms and no ongoing requirement for corticosteroids as therapy for brain metastases.

3.1.4 Patients with **untreated or progressive brain metastases** (active brain metastases) are eligible if the treating physician determines that immediate CNS specific treatment is not required and is unlikely to be required during the first cycle of therapy. There must be no ongoing requirement for corticosteroids as therapy for brain metastases.

3.1.5 Previous radiation, including whole brain radiation, is allowed  $\geq 7$  days of study registration. Stereotactic radiation therapy within 7 days is permitted.

3.1.6 Patients must have measurable disease by RECIST v1.1. At least one measurable lesion should be extra-cranial and outside of any portal of irradiation.

3.1.7 Archival tissue must be available or patients must be willing to undergo a new biopsy to provide pre-treatment tumor sample (no intervening chemotherapy treatment, tissue must be from current extensive-stage/metastatic diagnosis). See section 5.5.1 and 5.5.2 for tissue requirements.

3.1.8 Age  $\geq 18$  years.  
Because no dosing or adverse event data are currently available on the use of entinostat in combination with atezolizumab, carboplatin and etoposide in patients  $<18$  years of age, children are excluded from this study.

3.1.9 ECOG performance status  $\leq 2$  (Karnofsky  $\geq 60\%$ , see Appendix A).

3.1.10 Patients must have adequate organ and marrow function as defined below:

- absolute neutrophil count	$\geq 1,500/\text{mcL}$
- hemoglobin	$\geq 9.0 \text{ g/dL}$
- platelets	$\geq 100,000/\text{mcL}$
- INR	$<1.5$
- total bilirubin	$\leq 1.5 \times$ institutional upper limit of normal (ULN).

		(This does not apply to patients with confirmed Gilbert's syndrome)

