## 6. TREATMENT PLAN

### 6.1 Agent Administration

Treatment will be administered on an outpatient basis (inpatient is allowed if clinically indicated). Reported adverse events and potential risks are described in Section 10. Appropriate dose modifications are described in Section 7. No investigational or commercial agents or therapies other than those described below may be administered with the intent to treat the patient's malignancy.

Patients will receive up to 4 cycles of induction treatment followed by maintenance treatment for a total of 1 year of combined treatment (or 17 cycles). Patients who are unable to tolerate carboplatin and etoposide may discontinue induction and receive maintenance treatment for the remaining duration of treatment. Order of administration during induction should be according to institutional standard. Entinostat should be taken prior to administration of other agents.

On day 1, when patient receives additional therapy, entinostat will be administered prior to other chemotherapy or immunotherapy agents. On day 1 of induction cycles, Atezolizumab will be administered first, followed by carboplatin, and lastly etoposide. Time intervals between infusions are per institutional standards.

Dose Escalation Schedule								
Dose Level	Induction (Cycles 1-4)				Maintenance (Cycles 5-17)		Cycle Length	
	Dose				Dose			
	Carboplatin	Etoposide	Atezolizumab	Entinostat	Atezolizumab	Entinostat		
Level -1 (ME)	AUC 5 IV D1	100 mg/m  IV D1-3	1200 mg IV D1	None	1200 mg IV D1	5 mg PO D1, 8, 15	21 days	
Level 1*	AUC 5 IV D1	100 mg/m  IV D1-3	1200 mg IV D1	2 mg PO D1, 8, 15	1200 mg IV D1	5 mg PO D1, 8, 15	21 days	
Level 2	AUC 5 IV D1	100 mg/m  IV D1-3	1200 mg IV D1	3 mg PO D1, 8, 15	1200 mg IV D1	5 mg PO D1, 8, 15	21 days	
Level 3	AUC 5 IV D1	100 mg/m  IV D1-3	1200 mg IV D1	5 mg PO D1, 8, 15	1200 mg IV D1	5 mg PO D1, 8, 15	21 days	

\*Starting Dose Level.

IV = intravenous, AUC = Area Under Curve, PO = Orally, ME = Maintenance entinostat.

Regimen Description – Induction (up to 4 cycles) #					
Agent	Premedication; Precautions*	Dose	Route	Schedule	Cycle Length
Entinostat	Take on an empty stomach (at least 1 hour before and 2 hours after a meal)	Assigned dose level	PO	Day 1, 8, 15	21 days (3 weeks)
Atezolizumab		1200 mg	IV infusion over 60 ( $\pm 15$ ) minutes**	Day 1	
Carboplatin	Dexamethasone NK1 antagonist 5-HT3 antagonist.	AUC 5***	IV infusion over 30-60 minutes	Day 1	

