## 6.2 Definition of Dose-Limiting Toxicity

Management and dose modifications associated with the above adverse events are outlined in Section 7.

Dose limiting toxicity (DLT) is defined as the occurrence of any of the following toxicities listed below. The DLT period will be from Cycle 1, Day 1 through the first cycle. To be evaluable for a DLT, at least 66% of the prescribed dose of each drug must be received during cycle 1 (i.e., 2 of 3 doses of entinostat must be received or 66% of prescribed carboplatin, etoposide, or atezolizumab dose must be infused to be considered evaluable if no DLT occurred). If treatment-related adverse events result in <66% of drug doses received, patients will be evaluable for DLTs. Any toxicities attributable to cancer or cancer progression will not be considered DLTs.

DLTs if felt to be possibly, probably, or definitely related to entinostat:

- Less than 66% of entinostat (0 or 1 doses) received during the first cycle due to treatment-related adverse event(s)
- Death in the absence of progressive cancer (Any grade 5 adverse event)
- Any adverse event resulting in discontinuation of carboplatin/etoposide chemotherapy prior to Cycle 2
- Any treatment-related toxicity causing delay of more than 3 weeks from planned cycle 2 day 1
- Any  $\geq$  Grade 3 non-hematologic adverse event (non-laboratory), excluding alopecia, uncontrolled nausea or vomiting. Grade  $\geq 4$  uncontrolled nausea or vomiting should be considered a DLT if it persists  $\geq 72$  hours despite maximal medical management.
- Any  $\geq$  Grade 3 non-hematologic laboratory value if medical intervention is required (not including endocrinopathies requiring hormone replacement) or leads to hospitalization

DLTs regardless of relatedness to entinostat (attribution to any study drug):

- Hematologic events
  - Grade  $\geq 4$  febrile neutropenia
  - Grade 4 neutropenia lasting  $>7$  days
  - Grade 3 thrombocytopenia associated with bleeding requiring transfusion or Grade  $\geq 4$  thrombocytopenia.

Dose escalation will proceed within each cohort of 3 patients according to the following scheme. Dose-limiting toxicity (DLT) is defined above.

Escalation/De-escalation Rule												
Number of patients treated	1	2	3	4	5	6	7	8	9	10	11	12
Escalate if # of DLT $\leq$	0	0	0	0	0	0	1	1	1	1	1	1
Deescalate if # of DLT $\geq$	1	1	1	1	2	2	2	2	3	3	3	3
Eliminate if # of DLT $\geq$	NA	NA	2	3	3	3	4	4	4	5	5	5

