### 7.1 Carboplatin and Etoposide

The following hematologic parameters must be met on **Day 1** of Cycles 1-4:

- Absolute neutrophil count (ANC)  $\geq 1500/\text{mm}^3$
- Hemoglobin  $\geq 8.0 \text{ g/dL}$
- Platelets  $\geq 100/\text{mm}^3$

If Day 1 parameters are not met and carboplatin and etoposide are held, all Day 1 treatments (carboplatin, etoposide, atezolizumab, and entinostat) will be delayed until parameters are met.

If delays  $>3$  weeks are required before carboplatin and etoposide can be resumed, induction will be discontinued. The patient may then initiate the maintenance regimen. Alternatively, the patient may discontinue all study treatment and standard of care atezolizumab may be continued per investigator discretion.

Supportive therapy with granulocyte colony stimulating factor (GCSF) in order to achieve Day 1 treatment parameters may be used per ASCO or NCCN guidelines.

Dose modifications for carboplatin and etoposide should be conducted per investigator discretion based on institutional standards and guidance from package inserts for each drug. In general, when dose modifications to entinostat are required (e.g., for hematologic adverse events), dose reductions for carboplatin and etoposide should strongly be considered unless the adverse event is clearly attributable to entinostat alone.

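### Section 6.3.2.2 prohibits starting or increasing G-CSF in patients with solid malignancies, Sections 7.1 and 7.2.3 allow it, and nothing says which rule governs

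*Combined protocol and SAP*

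**What the plan says.** **Against G-CSF.** Section 6.3.2.2 lists therapies to avoid with atezolizumab. One bullet says that initiating or increasing the dose of granulocyte colony stimulating factors, with examples ending "granulocyte/macrophage colony stimulating factor, and/or pegfilgrastim) is prohibited for patients with solid malignancies". The list containing that bullet opens with "It is strongly recommended that", so the lead-in advises while the bullet forbids.

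**For G-CSF.** Section 7.1, on the Day 1 requirements of Cycles 1-4, states: "Supportive therapy with granulocyte colony stimulating factor (GCSF) in order to achieve Day 1 treatment parameters may be used per ASCO or NCCN guidelines". Section 7.2.3 adds two provisions in its neutropenia table. A footnote lets entinostat resume one dose level lower, with G-CSF support, once a mid-cycle Grade 4 event has recovered to Grade 1 or less; it sets no cycle limit. A note on neutropenia between days 2 and 21 that improves by the next Day 1 says G-CSF should be considered in later cycles.

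**Who is covered.** Section 3.1.1 admits ES-SCLC or "other solid tumors for which carboplatin and etoposide are considered appropriate therapy". Atezolizumab is part of every dose level in the Section 6.1 table. Both sets of rules therefore apply to the same patients.

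**Links between the sections.** Section 6.1 says "Appropriate dose modifications are described in Section 7". Section 6.2 says "Management and dose modifications associated with the above adverse events are outlined in Section 7". Neither mentions 6.3.2.2 or makes an exception to it.

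**The concern.** Two parts of one protocol give opposite instructions on a common supportive drug, in a regimen whose hematologic toxicities the protocol itself expects to overlap (Sections 2.4.2.2 and 9.1). Section 6.3 is the concomitant medication and supportive care section, so a site checking whether G-CSF is allowed would naturally look there and find it named as prohibited.

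Three things are at stake:

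- **Cycles received.** Under Section 7.1, if the Day 1 counts are not met and chemotherapy is held, "all Day 1 treatments (carboplatin, etoposide, atezolizumab, and entinostat) will be delayed until parameters are met". A delay of more than 3 weeks ends induction. Withholding G-CSF could therefore reduce the number of four-drug cycles (primary endpoint, Section 9.1) and the proportion of patients receiving 3 or more (primary objective, Section 1.1.3).
- **DLT calls.** A treatment-related delay of more than 3 weeks from the planned Cycle 2 Day 1 is a DLT under Section 6.2 if at least possibly related to entinostat. Grade 4 neutropenia lasting more than 7 days is a DLT whichever study drug caused it. Section 6.2 does not mention G-CSF.
- **Entinostat resumption.** After mid-cycle Grade 4 neutropenia, a site that believes it may not give G-CSF cannot use the Section 7.2.3 footnote as written.

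**Working it through.** The point is a contradiction in text, and the plan has no figure of its own to reproduce. The check compares the provisions and then shows what one patient could be worth.

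**1. The provisions side by side**

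| Section | Situation | Instruction on G-CSF |
|---|---|---|
| 6.3.2.2 | Any patient with a solid malignancy, at any time on study | Starting or increasing is prohibited (list headed as a strong recommendation) |
| 7.1 | Reaching Day 1 counts, Cycles 1-4 | May be used, following ASCO or NCCN guidelines |
| 7.2.3, Grade 4 footnote | Resuming entinostat after a mid-cycle event | Resume one level lower with G-CSF support |
| 7.2.3, note below the table | Neutropenia on days 2-21, improved by next Day 1 | Should be considered in later cycles |

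**2. Can they be read together?**

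- *By population:* no. Every eligible patient has a solid tumor and receives atezolizumab.
- *By timing:* no. The prohibition has no time limit, so it includes Cycles 1-4 and every later cycle.
- *By strength of wording:* no. If the lead-in turns the bullet into a strong recommendation against G-CSF, it still opposes the Section 7.2.3 advice to consider it.
- *By precedence:* no. Sections 6.1 and 6.2 point to Section 7 for dose modifications and adverse event management, but neither says that Section 7 overrides a listed exclusion.

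**3. Which rule was probably intended?** Section 7, most likely. Its provisions are specific to this regimen, and the neighboring Section 6.3.2.1 still contains an unfilled template placeholder, the sentence ending "if applicable] should continue their use". That suggests the atezolizumab text was carried over. This is inference; the protocol does not say so.

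**4. Weight of one patient on the feasibility proportion**

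Section 9.3 reports the proportion receiving 3 or more cycles with a 90% confidence interval but does not state the denominator. Three assumptions are shown; the weight is 1/n.

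- Pooled over the maximum of 36 (Section 9.2): 1/36 = 2.8 points.
- Simulated average of 23.7 (Section 9.1.3, Scenarios 1 and 2): 1/23.7 = 4.2 points. The lower averages, 22.3 (Scenario 3) and 19.4 (Scenario 4), give 1/22.3 = 4.5 and 1/19.4 = 5.2 points.
- Twelve on one dose level (Section 9.2): 1/12 = 8.3 points.

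Exact (Clopper-Pearson) 90% intervals, with counts chosen only for illustration:

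| Count | Estimate | 90% CI |
|---|---|---|
| 30/36 | 83.3% | 69.7 to 92.5% |
| 29/36 | 80.6% | 66.6 to 90.5% |
| 10/12 | 83.3% | 56.2 to 97.0% |
| 9/12 | 75.0% | 47.3 to 92.8% |

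A one-patient shift lies well inside the interval in both cases.

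**5. Weight of one DLT.** In the Section 9.1.1 table, a cohort of 3 escalates with 0 DLTs and de-escalates with 1. A single delay-related DLT in a first cohort of 3 therefore reverses the dose decision.

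**The case against.** The strongest reply is that a reasonable reader would follow Section 7. Section 6.2 sends management of the listed adverse events there, and neutropenia is among them. Three specific provisions allow G-CSF, against one generic atezolizumab bullet that sits in a list of recommendations. The outright prohibition that opens 6.3.2.2 concerns anticancer therapy and does not reach G-CSF.

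The harm also needs several steps: a site must follow 6.3.2.2 over Section 7, a neutropenic delay must follow and exceed 3 weeks, and G-CSF must be what would have prevented it. Section 7.1 leaves carboplatin and etoposide dose modification to the investigator as another tool. The Section 7.2.3 note on days 2-21 may offer a way to resume entinostat without G-CSF. Section 6.3 requires all concurrent drugs to be recorded, and Section 13.1 provides for calls at least monthly, so differing practice would probably be noticed. The one-patient figures would apply to any proportion and say nothing about G-CSF itself. Pooling over 36 could also include Level -1 patients, who receive no entinostat during induction.

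Much of this stands. The force of the bullet is unclear, the consequences are conditional, and the figures give scale only. What does not follow is that the conflict disappears. A pointer to dose modification rules does not lift a named exclusion. Records and calls can reveal differing practice, but they do not change the written rule.

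**Conclusion.** The concern holds. As written, the protocol both prohibits and permits G-CSF for the same patients and sets no order of precedence. It should be fixed because a site obeying 6.3.2.2 would withhold care that Section 7 allows.

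The size of the effect on cycles received or on DLT counts cannot be estimated from the documents. The conclusion that the design is not threatened rests on the one-patient comparison, with assumed denominators and illustrative counts, and on the reading that Section 7 is probably what was meant. The text conflict itself rests on no assumption.

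**What to change.** In Section 6.3.2.2, either delete the G-CSF bullet or add an exception for use permitted in Sections 7.1 and 7.2.3. One rule then applies at every site, including during the Cycle 1 DLT window.

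Two additions are optional and not needed to resolve the conflict: a sentence in Section 6.2 saying whether primary G-CSF prophylaxis is allowed in Cycle 1, and a listing of hematologic DLTs by G-CSF use.

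The required change is one bullet or one phrase. It adds no patients, procedures or data collection and leaves the BOIN rules as they are.
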